3. INTRODUCTION AND RATIONALE

3.1. Rationale

Breast cancer is one of the most common cancer types among women around the world. Approximately one in eight American women will be diagnosed with breast cancer in her life time [1]. Early detection of cancer leads to a better prognosis with a bigger chance to survive the disease. As such, screening programs have been developed to identify non-palpable breast cancer in asymptomatic women with x-ray imaging. While there have been numerous technologies used for breast cancer screening, the gold standard since the late 1970s has been x-ray based mammography [2].

Population based mammography screening has in some studies been shown to reduce breast cancer mortality by between 40% and 45% [3]. Digital mammography has supplanted film-screen mammography during the last ten years and diagnostic performance of the newer technology has now been proven in several large studies [4]-[6]. Digital mammography enables efficiency improvements and opportunities of future advanced applications such as spectral imaging, tomosynthesis and phase contrast imaging.

Tomosynthesis provides a three-dimensional reconstruction of the breast which is of interest both for screening and diagnostic procedures. The image reconstruction enables cross-sectional visualization of the breast tissue reducing difficulties of interpretation of projection images of overlapping tissue or superposition.

3.2. Literature review

Tomosynthesis is intensively marketed by the major mammography vendors, notably Hologic, GE and Siemens. A growing body of clinical data supports increased cancer detection rates, and also in some locations, reduced non-cancer recall rates [7]. The technology has passed the early adopter phase and is now moving into the mass market. Recently it was reported that 30% of the radiologists in the US used tomosynthesis in their practice and that 62% of the remaining radiologists report that they planned to obtain it soon [8].

In spite of the trend towards fast adoption of tomosynthesis there are still many major markets where the transition from 2D mammography to tomosynthesis is still expected to take many years. Guidelines for quality control as well as standards for safety and essential performance are still works in progress for tomosynthesis. Furthermore screening guidelines and reimbursement systems do not yet support tomosynthesis in screening.

3.3. Device description

The investigational device, Philips MicroDose SI version S0, Tomosynthesis prototype system (referred to as Philips MicroDose Tomosynthesis here) is developed by Philips Digital Mammography Sweden AB, a Philips Healthcare company. The proposed Philips MicroDose Tomosynthesis system is a based on the same technology as the FDA cleared FFDM device, Philips MicroDose SI.

The investigational device includes MicroDose SI S0 Tomosynthesis system with software version 11.0.

The manufacturer of the investigational device is:
Philips Digital Mammography Sweden AB
[name]
[name]
Sweden

Philips Mammography Solutions Sweden	Clinical Investigation Plan Comparison of the Philips MicroDose Tomosynthesis System to 2D Digital Mammography	DOC-MTIN-9RWH8K- 8.0 Page 10 of 38
---	---	--

3.3.1. **Intended use of the investigational device during the investigation / Indications for Use statement.**

The intended medical purpose of the Philips MicroDose Tomosynthesis is to produce radiographic images of the human breast for the purpose of diagnostic and screening mammography. The Philips MicroDose Tomosynthesis system is intended to be used in the same clinical applications as 2D mammography systems.

The intended medical purpose of the investigational device is to collect clinical data to support the PMA submission for Digital Breast Tomosynthesis (DBT) device. The examination where the investigational device will be used is a standard 4-view mammogram, i.e., medio-lateral oblique (MLO) and craniocaudal (CC) views of each breast, performed on asymptomatic women to detect the presence of breast cancer. Repeat standard views might be done for technical reasons, such as inadequate compression, inadequate amount of included breast tissue, or over- or underexposure.

3.3.2. **Populations and indications for which the device is intended, including contraindications**

The digital tomosynthesis mammography system is intended to support examinations of the human breast of both women and men.

Women invited for screening are usually in the age of 40 to 70, depending on the local regulations. Patients coming for diagnostic examinations are of any adult age.

3.3.3. **Device description**

The design of the MicroDose Tomosynthesis system is based on the currently marketed MicroDose SI L50, which was cleared by FDA via K123995 – February 1, 2013. Due to the close similarity of the two devices, most design features that are described in the 510(k) are applicable to the MicroDose Tomosynthesis system as well.

Philips Mammography Solutions Sweden	Clinical Investigation Plan Comparison of the Philips MicroDose Tomosynthesis System to 2D Digital Mammography	DOC-MTIN-9RWH8K- 8.0 Page 11 of 38
---	---	--

[figure not shown]

Figure 1. Overview of the MicroDose Tomosynthesis system.

Like the currently marketed MicroDose SI L50, the MicroDose tomosynthesis system consists of an acquisition workstation, a main cabinet and a side cabinet. With the exception of the side cabinet, these components are shown in Figure 1. In fact, these parts are the same in both systems. The main difference between the MicroDose Tomosynthesis system and the currently marketed MicroDose SI Model L50 is the design of the C-arm.

3.3.4. Pre-clinical testing

The product development project of the MicroDose Tomosynthesis system will be managed according to applicable parts of the Philips Digital Mammography's Product Development Process. The design will be verified according to the design verification processes on the first MicroDose Tomosynthesis system. The subsequent systems will be produced by limited production processes. To ensure that the subsequent systems will comply with the verified design, a predefined amount of test, selected via impact analysis, will be performed on each system. All risk related requirements will be verified on all systems.

The pre-clinical testing will put specific focus on image and radiation quality. The image quality tests include (but are not limited to) tests of exposure time, image areas, detector linearity, scatter rejection, spatial resolution, contrast-to-noise and signal-to-noise ratios, tests of the automatic exposure control, image homogeneity, contrast-detail resolution, and the Mammographic Accreditation Phantom. The radiation quality tests include (but are not limited to) tests of the tube output and generator accuracy, dose, half value layer, x-ray field, leakage radiation and protective shielding .

Philips Mammography Solutions Sweden	Clinical Investigation Plan Comparison of the Philips MicroDose Tomosynthesis System to 2D Digital Mammography	DOC-MTIN-9RWH8K- 8.0 Page 12 of 38
---	---	--

Regular quality control (QC) will be performed on the system according to a protocol aligned with the most recent version of the EUREF quality control procedures.

Change control will be performed according to applicable development processes. Issues found during verification and validation will be registered in a project issue database handled by a cross functional team (change control board). In addition to the internal testing described above, compliance verification will be conducted both in-house and by third party test house Intertek.

3.3.5. Device risk analysis and risk assessment

The risk management procedure is followed for the project. After performing risk analysis of the Philips MicroDose Tomosynthesis system, there are certain identified residual risks with justification. These risks are mainly related to software, x-ray exposure, moving parts during image acquisition, electronics of the photon-counting detector and high voltage used for X-ray.

A significant part of the identified justified risks are related to software. The technology of producing high quality digital images from a photon-counting imaging system can only be solved with software, for example image processing algorithms, image acquisition, data storage and data transfer, which are critical functions to the system performance. We still consider the risks of the system to be as-low-as-reasonably-practicable.

The scanning collimator is a necessary function when using multi-slit beam geometry to receive a tomosynthetic motion. This geometry reduces the dose to the examined patients. In summary, the benefit of Philips MicroDose overweighs the related risks.

3.3.6. Conclusion

The benefit of the study is to enable new technology that potentially could increase early detection and reduce breast cancer mortality. Furthermore the technology is also expected to reduce radiation dose level compared to existing commercially available flat panel systems.

As the subjects enrolled in the study will be imaged both with tomosynthesis and conventional 2D mammography, additional lesions could be detected in the screening patients that would not have been found only with conventional 2D mammography. However a direct benefit of the enrolled subjects is not expected. Possibly a missed cancer on the 2D mammogram could be detected on the tomosynthesis image. Another scenario is that a benign lesion is detected which could require additional imaging or even biopsy. The tomosynthesis images alone will not be used to make a decision to biopsy, but further work-up of such lesions with conventional imaging might indicate the need for biopsy. If a lesion is found on the tomosynthesis images but not detected on 2D, the radiologist at site might want to do additional imaging to assess the lesion. For the majority of the enrolled patients in the study, there will be no direct benefit as of participating in the study, though it is possible that a cancer that is missed on the 2D might be detected.

A risk that the enrolled subjects in the study are taking when participating in the study, is that they will be exposed to additional radiation. The radiation of the investigations device is comparable to Philips MicroDose SI, which is a low dose digital mammography system (approx. 0.8 mGy per view for a standard examination).

Philips Mammography Solutions Sweden	Clinical Investigation Plan Comparison of the Philips MicroDose Tomosynthesis System to 2D Digital Mammography	DOC-MTIN-9RWH8K- 8.0 Page 13 of 38
---	---	--

4. OBJECTIVES AND HYPOTHESES

4.1. Primary Objective

The primary objective of the study is to compare the safety and clinical performance of the Philips MicroDose Tomosynthesis system (Tomosynthesis and synthetic 2D) images to conventional 2D mammography images (FFDM).

Clinical performance will be based on the Area under the Receiver Operating Characteristics (ROC) Curve. The ROC curves will be generated using the confidence scores (CS) based on a numeric scale. ROC curves will be calculated for each reader.

The following hypothesis will be evaluated:

Null Hypothesis: $H_0: \Theta_2 - \Theta_1 \geq \Delta$
Alternative Hypothesis: $\Theta_2 - \Theta_1 < \Delta$

Where Θ_1 (Philips) and Θ_2 (FFDM) are the area under the Receiver Operating Characteristic (ROC) curve (AUC) for radiologists interpreting mammograms obtained on the Philips MicroDose Tomosynthesis system or FFDM, respectively. Delta (Δ) is the chosen non-inferior margin of 0.05.

4.2. Secondary Objectives

The secondary objectives are:

- To compare the average glandular dose for exams acquired on Philips MicroDose Tomosynthesis system and the 2D mammography system.
- To compare the non-cancer recall rate for Philips MicroDose Tomosynthesis system and 2D mammography exams.
- To compare the sensitivity and specificity of the Philips MicroDose tomosynthesis system (i.e., Tomosynthesis and synthetic 2D) to that obtained with 2D mammography.

The average glandular dose (AGD) will be recorded per subject for each breast (right and left) and view (CC and MLO). The following hypothesis will be evaluated:

- Null Hypothesis: $H_0: \mu_2 - \mu_1 > \delta$
- Alternative Hypothesis: $\mu_2 - \mu_1 \leq \delta$

where μ_1 and μ_2 are the mean average glandular dose (i.e., radiation dose) for the Philips MicroDose Tomosynthesis system and FFDM system, respectively, and δ is 10% of the FFDM radiation dose.

The non-cancer recall rate will be recorded per subject. The following hypothesis will be evaluated:

- Null Hypothesis: $H_0: \pi_2 - \pi_1 = 0$
- Alternative Hypothesis: $\pi_2 - \pi_1 \neq 0$

where π_1 and π_2 are the non-cancer recall rate for the Philips MicroDose Tomosynthesis system and FFDM system, respectively.

Sensitivity will be estimated for each reader as the proportion of cancer cases with per-case BI-RADS category 4 or higher. Specificity will also be estimated by reader as the proportion of non-cancer cases with per-case BI-RADS category less than 4. Ground truth will be based on biopsy results or the outcome for the woman after one year follow-up.

4.3. Supplementary Objectives

The following supplementary objectives will be evaluated:

Philips Mammography Solutions Sweden	Clinical Investigation Plan Comparison of the Philips MicroDose Tomosynthesis System to 2D Digital Mammography	DOC-MTIN-9RWH8K- 8.0 Page 14 of 38
---	---	--

- To evaluate the effect of breast density on AUC for images obtained using the Philips MicroDose Tomosynthesis system and 2D mammography system. Breast density will be stratified as fatty (i.e., BI-RADS breast density type A and B) and dense (BI-RADS breast density type C and D).
- To compare the average image interpretation time for exams performed with Philips MicroDose Tomosynthesis system and 2D mammography.
- To assess the diagnostic performance of the Philips MicroDose Tomosynthesis compared to the FFDM

5. STUDY DESIGN

5.1. General

The study is a multicenter, multi-case, multi-reader (MCMR) study with paired image acquisition and reader evaluation. The study will be performed in two phases: Imaging Accrual phase and Imaging Reading phase.

Approximately 800 women who fulfill all inclusion and exclusion criteria will be enrolled in chronological order from approximately 3 different US sites with one study investigator for each site. Two cohorts of patients will be enrolled (i.e., Biopsy and Screening Cohorts). Paired sets of a standard 4-view synthetic 2D and tomosynthesis slices exposed on Philips MicroDose Tomosynthesis system and 4-view mammograms on a FDA cleared FFDM system will be collected. All enrolled cases will be quality controlled for completeness of image and patient information.

A subset of the images collected as part of this study will also be used to validate the spectral breast density measurement. This validation is specified in a separate study protocol [9].

Depending on the experience at the sites, each site could also enroll up to 10 additional women to train the technologists on using the system and whose images will be used for training purposes. These cases will not be used in the reader study. In addition to these cases, images for reader training will be available that have been previously collected under another IRB approved protocol.

Approval for the study will be obtained from the ethics committees for all participating centers. All eligible subjects will provide written informed consent prior to entry into the study, which is defined as being imaged on the Philips MicroDose Tomosynthesis system and an FFDM system. Subject enrollment will be monitored by the sponsor at each site. All subjects will be consecutively enrolled.

All subjects interested in participating in the study will be assigned a unique study identification number. At the time of providing informed consent, subjects will be assigned the next number in sequence from the list of study identification numbers. After study enrollment, subjects will be identified solely by their study identification number on the Case Report Forms (CRF). In addition, all subject specific information will be removed from the images prior to them being electronically submitted to the study sponsor and only the subject's study identification number will be provided. Each participating site will maintain a database linking the study number to subject identification.

To protect against any bias during the imaging acquisition, the order in which the subject is imaged on either the investigational device or the FFDM will be randomized, except for patients that have undergone a screening exam including 2D. In this case, the patient will be imaged only with the Philips MicroDose Tomosynthesis system (since the 2D mammogram has been acquired previously). Reimaging will only be performed if more than 45 days have passed since the original acquisition. A randomization list will be generated for each cohort (i.e., the biopsy and screening cohort).

The mode of the eligibility screening exam (source) will be recorded. To protect from case selection bias, not more than 60% of the cases in the reader study can originally be screened with 2D or tomosynthesis. In this aspect combo screening (2D + tomosynthesis) is regarded as tomosynthesis.

The enrollment and randomization flow for each cohort is presented in Figure 2.

[figure not shown]

Figure 2: Patient Enrollment and Randomization by Cohort

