5.3.1. Inclusion criteria

- Patient is female and at least 40 years of age
- No contraindication for routine bilateral mammography

Philips Mammography Solutions Sweden	Clinical Investigation Plan Comparison of the Philips MicroDose Tomosynthesis System to 2D Digital Mammography	DOC-MTIN-9RWH8K- 8.0 Page 16 of 38
---	---	--

Screening Cohort

- Patient presents for a routine screening mammogram

Biopsy Cohort

- Patient is scheduled for a biopsy
- Patient has a screening detected abnormality

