5.4. Procedures

5.4.1. Image Accrual

The subjects will be recruited to either the biopsy cohort or the screening cohort as discussed in section 5.1. If the inclusion/exclusion criteria are met for either cohort, the subject will be asked to

Philips Mammography Solutions Sweden	Clinical Investigation Plan Comparison of the Philips MicroDose Tomosynthesis System to 2D Digital Mammography	DOC-MTIN-9RWH8K- 8.0 Page 17 of 38
---	---	--

participate in the study. The enrollment procedure will include study brief, inclusion/exclusion criteria, informed consent, randomization and data base entry (using a CRF). If the subject has no prior 2D screening exam, she will be randomized to either be imaged first on the investigational device and thereafter on the FFDM system, or the other way around. Imaging will be acquired by a trained technologist at site. Data management will be performed by a study assistant from each site; this includes anonymization, export, updated CRF etc.

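### Acquisition order is not randomised for women already screened with 2D, so for some cancers FFDM precedes detection and the Philips exam follows it, with no stated masking of the technologist

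*Combined protocol and SAP*

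**What the plan says.** Section 5.1 states the aim of order randomisation: "To protect against any bias during the imaging acquisition, the order in which the subject is imaged" is assigned at random. The same sentence carries the exception, which covers women whose screening exam included 2D: "the order in which the subject is imaged on either the investigational device or the FFDM will be randomized, except for patients that have undergone". For those women, "In this case, the patient will be imaged only with the Philips MicroDose Tomosynthesis system (since the 2D mammogram has been acquired previously"). Section 5.4.1 repeats the rule from the other side: "If the subject has no prior 2D screening exam, she will be randomized to either be imaged first on the investigational device" or first on FFDM.

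Three further provisions bear on the point:

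- Section 5.1 has a re-imaging rule: "Reimaging will only be performed if more than 45 days have passed since the original acquisition". It does not say which exam is repeated.
- Section 5.1 records the mode of the screening exam and sets a cap against case selection bias: "not more than 60% of the cases in the reader study can originally be screened with 2D or tomosynthesis". A combined 2D and tomosynthesis screen counts as tomosynthesis for this cap.
- Section 5.3.1 defines the biopsy cohort by an abnormality found at screening and by "Patient is scheduled for a biopsy".

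Images are taken by a trained site technologist (5.4.1). Standard views may be repeated for technical reasons, one of which is "inadequate amount of included breast tissue" (3.3.1). Readers receive no history or clinical data (5.4.2).

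**The concern.** The plan names order randomisation as its protection against acquisition bias, then removes it for a group in which order and knowledge of the lesion coincide. An exempt biopsy-cohort woman had her FFDM when nobody knew of a lesion. Her Philips exam comes when the lesion has been found and a biopsy booked. A technologist who knows the side or location could, even without intending to, position for it or repeat a view more readily, and only on the investigational device.

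The primary test is non-inferiority on reader-averaged AUC with a margin of 0.05. Any help given to one set of images at acquisition enters that comparison as if it were device performance. Blinding the readers cannot undo it, because the difference is already in the images.

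**Working it through.** The plan gives no figure on this point to reproduce. The check sets the provisions side by side, then asks what share of cancers is involved and how much leverage a single cancer has.

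**Step 1. Timing relative to detection, biopsy cohort**

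| Screening exam | FFDM used in the reader study | Philips exam | Order randomised? |
|---|---|---|---|
| 2D only, not re-imaged | before detection | after | no |
| Combined 2D and tomosynthesis, not re-imaged | before detection | after | no |
| Either of these, FFDM repeated after 45 days | after detection (if FFDM is the exam repeated) | after | not stated |
| Tomosynthesis alone | after detection | after | yes |

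The imbalance is confined to the first two rows.

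**Step 2. Share of the 65 cancers in those rows**

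Share = (p + (1 − p) × c) × (1 − r), where p is the share screened with 2D only, c the share of the remainder who had a combined exam, and r the share whose FFDM is repeated. None of the three is in the documents, so all are assumptions. The formula also treats every cancer as coming from the biopsy cohort; cancers first found in the screening cohort would lower the result.

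If the 60% cap is read as applying to each mode, if the two modes cover all cases, and if the cap happened to hold among the cancers, p runs from 0.40 to 0.60, or 26 to 39 of 65. With p = 0.5:

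| | r = 0 | r = 0.2 | r = 0.4 |
|---|---|---|---|
| c = 0 | 50% | 40% | 30% |
| c = 0.25 | 63% | 50% | 38% |
| c = 0.5 | 75% | 60% | 45% |

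The cap does not in fact bind the cancers. It applies to all 300 + 65 + 40 = 405 reader cases: 0.60 × 405 = 243 and 0.40 × 405 = 162. Since 65 is below 162, the cancers could all be of one screening mode, or none of them, with the cap still met. Cancer strata in 5.4.6.3 are lesion type, density and size, not screening mode.

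**Step 3. Leverage of one cancer**

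In the empirical AUC, a change d in one cancer's percentile among the non-cancers moves the AUC by d/65. Taking d = 0.6 in every reader (for example 0.3 to 0.9, an assumption):

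- one cancer: 0.6/65 = 0.009, or 18% of the 0.05 margin;
- three cancers: 1.8/65 = 0.028, or 55% of the margin;
- one cancer, with only half the readers affected: 0.3/65 = 0.005.

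This shows leverage only. It does not estimate a bias.

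**Step 4. Would the analysis show it?**

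Section 6 has no analysis by acquisition order or screening mode. The recorded screening mode would not be enough: because of the 45-day rule, mode alone does not show whether the FFDM that was read predates the study.

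**The case against.** The strongest case on the other side has five parts.

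- *The net direction may be the reverse.* A woman screened with 2D alone enters the biopsy cohort because that FFDM showed something. Such cancers are selected for being detected on the comparator, which favours FFDM and works against a non-inferiority pass. This stands. A reader might infer that the exemption pushes towards a false pass; the documents do not support that, because two opposing mechanisms act in the same women and neither is quantified.
- *The number of cancers is not known.* A reader might infer that most cancers are affected. That does not follow: the share is not given, the 45-day rule may move some FFDM exams to after detection, and women screened with tomosynthesis alone are still randomised. This stands.
- *The mechanism is narrow.* The exam is four standard views, repeats are for technical reasons only, and no text permits lesion-directed or extra views. This limits the possible effect to positioning and repeats, but does not exclude it.
- *Lack of masking is inferred from silence.* Figure 2, the enrolment and randomisation flow, is not reproduced in the available text. That is a fair caution, although its title does not suggest that it covers technologist masking.
- *The cap already addresses source-exam bias.* It addresses case selection, over all cases, and counts combined screens as tomosynthesis although they include 2D and so trigger the exemption. It does not close this gap.

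**Conclusion.** The gap is real but limited. For biopsy-cohort cancers screened with an exam that included 2D and not re-imaged, the order is fixed as FFDM before detection and Philips after, and no visible provision masks the technologist. This rests on the text of 5.1, 5.3.1 and 5.4.1 and needs no assumption beyond reading silence on masking as absence.

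The extent is not known. The affected group could be a minority or a majority of the 65 cancers, depending on three shares that the documents do not give. The size of any effect is unknown, and its net direction is open. The figure of 0.009 per cancer shows only that a few cancers can matter against a margin of 0.05. The point supports a low-cost improvement, not a conclusion that the primary comparison is invalid.

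**What to change.** In sections 5.1 and 5.4.1:

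1. Require that, for biopsy-cohort women, the technologist is not given the prior images, the lesion side or the lesion location until the four standard Philips views have been accepted.
2. Log every repeated view with its technical reason.
3. Add one CRF flag per reader case with two values: FFDM acquired before the study, or both exams acquired in the study.

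In section 6, pre-specify a descriptive report of the primary AUC difference by this flag. State with it that the estimates will be imprecise with 65 cancers, and that the flag is confounded with the mode of detection, so a difference between groups could not be attributed to acquisition knowledge alone.

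The cost is a site instruction, a repeat log, one data field and one table, with no added imaging or staff. The downsides are slightly more handling at the visit and imperfect masking, since the woman herself knows the side.
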